6.6. SAFETY ANALYSIS

Descriptive summaries will be generated for select safety data including treatment-emergent adverse events, changes from baseline in selected laboratory assessments, and worst QTcF interval. All adverse events will be graded for severity using NCI-CTCAE v5.0. Toxicities that are not specified in the NCI-CTCAE will be graded for severity as follows:

- Grade 1 (Mild): asymptomatic or mild symptoms; clinical or diagnostic observation only; intervention not indicated
- Grade 2 (Moderate): minimal, local or non-invasive intervention indicated; limiting age-appropriate instrumental activities of daily living (ADL)
- Grade 3 (Severe): Medically significant but not immediately life-threatening; hospitalization or prolongation of hospitalization indicated; disabling; limiting self-care ADL

- Grade 4 (Life-threatening): Urgent intervention indicated required to remove or abrogate risk of death
- Grade 5: Death related to AE

6.6.1. Adverse Events

Adverse events will be mapped to the MedDRA version in effect at the time of database lock.

TEAEs will be reported by dose level and overall. .

If a patient experiences multiple events that map to a single preferred term, the event of greatest severity will be assigned to the preferred term for the appropriate summaries. Patients with events mapping to multiple preferred terms within the same system organ class will be counted once at the system organ class level.

TEAEs will be summarized by treatment group using PT and SOC. Separate summaries of Grade 3 and 4 treatment-emergent adverse events, treatment-emergent serious adverse events (TESAEs), TEAEs related to LANRA, and events leading to treatment interruption, dose reduction, treatment discontinuation or death will be generated. All adverse events reported will be listed for individual patients showing both verbatim and preferred terms.

Missing onset dates will be imputed as previously outlined in [Section 4.4.4.4](#).

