### 2.2.1 Gilteritinib:

Gilteritinib is a small-molecule, oral FLT3 inhibitor with highly specific and potent inhibition of FLT3 receptors with both ITD and D835 mutations (either alone or in combination) (Mori et al, 2017; Lee et al, 2017). *In vivo*, gilteritinib inhibited tumor growth and induced tumor regressions in mice xenografted with MV4-11 AML cells (Mori et al,

2017). A Phase 1/2 dose-escalation/expansion study (the CHRYSALIS study) evaluated the safety/tolerability, pharmacokinetic (PK), and antileukemic activity of once-daily gilteritinib as a single agent at doses of 20–450 mg in patients with R/R, *FLT3*-wild type (n=58) or *FLT3*-mutated AML (n=194) (James et al, 2020; Perl et al, 2017). Gilteritinib was well tolerated with a maximally tolerated dose (MTD) of 300 mg QD. Potent *FLT3* inhibition and dose-proportional PK were observed across all doses. Doses  $\geq$  80 mg/day were associated with  $>$  90% *FLT3* inhibition and an overall response rate of 52% (including 41% with CR, CRi [CR with incomplete blood count recovery] or CRp [CR with partial platelet count recovery]) among patients with *FLT3*-mutated disease (Perl et al, 2017) and a median OS of 31 weeks. The Phase 3 ADMIRAL trial compared the efficacy and safety of gilteritinib as a QD dose of 120 mg with standard, either high or low intensity, salvage chemotherapy in patients with *FLT3*-mutated, R/R AML. The median OS in the gilteritinib treated group was 9.3 months vs. 5.6 months for the chemotherapy-treated group (HR, 0.64; 95% CI, 0.49 to 0.83;  $P < 0.001$ ) (Perl et al, 2019). Thirty-four percent of patients achieved CR with full or partial hematologic recovery in the gilteritinib group compared with 15.3% in the chemotherapy group; the percentages of patients achieving CR were 21.1% and 10.5%, respectively. Grade  $\geq$ 3 adverse events (AEs) and serious adverse events (SAEs) occurred less frequently in the gilteritinib group than in the chemotherapy groups when adjusted for therapy duration. The most common Grade  $\geq$ 3 AEs in the gilteritinib group were febrile neutropenia (45.9%), anemia (40.7%), and thrombocytopenia (22.8%) (Perl et al, 2019). Results from the CHRYSALIS and ADMIRAL studies were the basis for the recent FDA and EMA approval of gilteritinib in patients with R/R, *FLT3*-mutated AML.

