**Table 1: Dose-escalation Scheme (Provisional)**

Dose Cohort (n):	LANRA Dose:	Gilteritinib Dose:
Cohort 1	20 mg QD	120 mg QD
Cohort 2	40 mg QD	120 mg QD
Cohort 3	60 mg QD	120 mg QD
Cohort 4	90 mg QD	120 mg QD

A “3 + 3” dose escalation scheme will be employed in which 1 DLT reported from among the first 3 evaluable patients in a dose cohort will prompt enrollment of 3 additional evaluable patients. More than 1 DLT attributed to LANRA among 6 patients evaluable for DLT would indicate an intolerable dose, thus rendering the most proximate lower dose with either 0 of 3 or 1 of 6 patients with LANRA-related DLTs the MTD. Dose-limiting toxicities are defined in [Appendix 1](#). The starting dose of LANRA is 20 mg QD (Cohort 1, Table 1). Enrollment will be staggered such that the first patient to enroll in a dose cohort will begin combination therapy on C1D2 (see below) and at least 24 hours before subsequent patients are enrolled to that cohort. All patients within a cohort (except those who discontinue in Cycle 1 due to DLT) must complete the DLT assessment period before a decision to begin testing the next higher dose. Enrollment of the next higher dose cohort will not proceed until a safety review has been completed for the preceding cohort(s) by a DEC consisting of

investigators with enrolled patients and sponsor representatives including (but not limited to) the medical monitor, safety officer, PK, and translational science leads. All decisions regarding dose escalation including declaration of the MTD/RP2D will be made by the DEC. The determination of whether or not to enroll the next higher dose cohort, enroll a lower dose cohort/add additional patients to a cohort previously cleared for safety/tolerability by the DEC or declare the MTD/RP2D will be based on available safety, PK, and PD data from all dose cohorts. If no protocol-defined MTD is identified for LANRA, the lowest dose that shows consistent evidence of adequate SYK inhibition based on PD assays will be deemed the RP2D ([Section 2.6](#)).

Patients will be evaluated for DLTs beginning on C1D1 up to and including safety assessments collected on Cycle 2, Day 1 for determination of LANRA MTD in combination with standard-dose gilteritinib. Patients will be evaluable for DLT in Phase 1b if one of the following occurs:

- They experience a DLT after receiving  $\geq 1$  dose of LANRA during the DLT assessment period.

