- Grade 4 neutropenia or thrombocytopenia lasting > 28 days after treatment onset that is not attributed to active AML and at least possibly related to LANRA.

- Any toxicity resulting in reduction in the dose of LANRA in Cycle 1.

*In general, infection will not constitute a DLT unless it is assessed as having resulted from unexpectedly prolonged myelosuppression in the setting of < 5% blasts in the bone marrow, absence of myelodysplastic changes, and/or absence of AML by flow cytometry in the bone marrow.

Adverse Event

An AE is defined as any unfavorable or unintended sign, symptom, laboratory abnormality or disease (new or exacerbated) temporally associated with the use of a study drug, whether considered causally related to the study drug or not.

All AEs defined as reportable in Section 16.6 of the protocol will be recorded on the ADVERSE EVENTS CRF.

Treatment-emergent Adverse Event (TEAE)

Any adverse event that occurs on or after C1D1 and up to the End-of-Treatment visit following discontinuation of the last study drug is considered treatment-emergent.

Events that occur after the initiation of non-protocol anti-leukemic therapy will be considered as non-treatment emergent even if they occur before the End-of-Treatment visit.

Treatment-emergent Laboratory Toxicity (TELT)

A TELT is identified based on the laboratory data recorded in the eCRF and is defined as a National Cancer Institute - Common Toxicity Criteria for Adverse Events (NCI-CTCAE) v5.0 (NCI 2017) grade 1 or higher abnormality, which occurs on or after C1D1 and up to the End-of-Treatment visit and exhibits at least 1 grade shift from the baseline value.

Events that occur after the initiation of non-protocol anti-leukemic therapy will be considered as non-treatment emergent even if they occur before the End-of-Treatment visit.

Concomitant Medications

Concomitant medications are those medications taken on or after C1D1. This includes medications started prior to C1D1 and continued after C1D1. These medications will be recorded in the PRIOR/CONCOMITANT MEDICATION eCRF.

Prior Medications

Prior medications are those medications taken from the time of informed consent until C1D1. These medications will be recorded in the PRIOR/CONCOMITANT MEDICATION eCRF.

End of Study

After all enrolled patients either relapse or die or 5 years after the last patient enrolls (whichever is earlier) or if the sponsor decides to terminate the trial.

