7. CHANGES IN THE PLANNED ANALYSES

The estimated total number of patients was increased from 35 to 100 to accommodate a potential 4th dose cohort in Phase 1b, to increase precision of the type 1 error to 0.025 (1-sided) in Phase 2 for the composite CR endpoint, and to allow for backfill patient enrollment. Eighty percent (80%) CIs for proportions of patients with CR/CRh, those with any CR (CR, CRh or CRi), medians and landmark rates for EFS and duration of response were increased to 95% to reflect the increase in estimated total number of patients.

In light of the Sponsor's decision to terminate the trial at completion of Phase 1b, all analyses, data summaries and listings will be restricted to results from Phase 1b patients only. Phase 2 was not be enrolled.

Following the completion of the protocol specified analyses as specified in this SAP, the sponsor may choose to conduct additional exploratory analyses. Such analyses will be detailed in a separate document.

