10. PROPOSED TABLES, LISTINGS, AND FIGURES

Tables	
14.1.1	Subject Disposition and Discontinuation Summary, All Patients Enrolled: Phase 1b
14.1.2.1	Demographics, Safety Population : Phase 1b
14.1.2.2	Baseline Disease Characteristics, Safety Population : Phase 1b
14.1.4.1	Summary of Exposure, Safety Population: Phase 1b
14.1.4.2	Summary of Prior Antileukemic Regimens, Safety Population: Phase 1b
14.2.1	Summary of Best Response by ELN 2017 response criteria, Efficacy Evaluable Population: Phase 1b
14.2.2	Overall Survival, Safety Population: Phase 1b
14.3.1.1	Overview of Treatment Emergent Adverse Events, Safety Population: Phase 1b
14.3.1.2	Treatment-Emergent Adverse Events by System Organ Class, Preferred Term (All Cycles), Safety Population: Phase 1b
14.3.1.3	Treatment-Emergent Non-Serious Adverse Events by System Organ Class, Preferred Term (All Cycles), Safety Population: Phase 1b
14.3.1.4	Grade 3 or 4 Treatment-Emergent Adverse Events by System Organ Class, Preferred Term and Greatest Severity (All Cycles), Safety Population: Phase 1b
14.3.1.5	Treatment-Emergent Serious Adverse Events by System Organ Class, Preferred Term (All Cycles), Safety Population: Phase 1b
14.3.1.6	Treatment Related Adverse Events by System Organ Class, Preferred Term (All Cycles), Safety Population: Phase 1b

14.3.1.7	Treatment Emergent Adverse Events Leading to Dose Reduction by System Organ Class, Preferred Term (All Cycles), Safety Population: Phase 1b
14.3.1.8	Treatment Emergent Adverse Events Leading to Treatment Discontinuation by System Organ Class, Preferred Term (All Cycles), Safety Population: Phase 1b
14.3.1.9	Treatment Emergent Adverse Events Leading to Death by System Organ Class, Preferred Term (All Cycles), Safety Population: Phase 1b
14.3.2	Select Grade 3 or 4 Treatment-Emergent Laboratory Toxicities, All Cycles, Safety Population: Phase 1b
14.3.3	Electrocardiogram by Worst QTcF Results: Phase 1b
Listings	
16.2.1	Subject Disposition, All Patients Enrolled: Phase 1b
16.2.2.1	Informed Consent, All Patients Enrolled: Phase 1b
16.2.2.2	Subject Eligibility, All Patients Enrolled: Phase 1b
16.2.3	Analysis Populations, All Patients Enrolled: Phase 1b
16.2.4.1	Demographics, All Patients Enrolled: Phase 1b
16.2.4.2	General Medical History, All Patients Enrolled: Phase 1b
16.2.4.3	AML Diagnosis, All Patients Enrolled: Phase 1b
16.2.4.4	Additional AML Details, All Patients Enrolled: Phase 1b
16.2.4.5	Prior Systemic Anti-Leukemia Regimens, All Patients Enrolled: Phase 1b

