 - ◆ For categorical variables that are presented in frequency tables, the module should present the total count in addition to the count in each category. Percentages should be calculated using this total as the denominator, and the percentage corresponding to the sum itself (that is, 100%) should be presented so as to indicate clearly to a reviewer the method of calculation.
- Sorting: Listings will be sorted by treatment group, patient number and date, if applicable. If a listing is sorted in a different manner, a footnote will indicate as such.

- General formatting rules: Rounding for all variables will occur only as the last step, immediately prior to presentation in listings, tables, and figures. No intermediate rounding will be performed on derived variables. The standard rounding practice of rounding numbers ending in 0-4 down and numbers ending in 5-9 up will be employed.
- The presentation of numerical values will adhere to the following guidelines:
 - ◆ Raw measurements will be reported to the number of significant digits as captured electronically or on the eCRFs.
 - ◆ Standard deviations will be reported to two decimal place beyond the number of decimal places the original parameter is presented.
 - ◆ Means, medians, first and third quartiles will be reported to one decimal place beyond the number of decimal places in the original parameter presented.
 - ◆ Calculated percentages will be reported with no decimals.
- Dates will be formatted as DDMMYYYY. Partial dates will be presented on data listings as recorded on CRFs.
 - Time will be presented according to the 24-hour clock (HHMM).

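### Crude adverse event percentages by dose run over patient-specific windows that may differ between dose groups, and no common-window adverse event table is planned

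*SAP*

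**What the plan says.** - **Reporting by dose.** SAP 6.6.1: "TEAEs will be reported by dose level and overall". The Phase 1b primary endpoint (SAP Section 3) includes the incidence and severity of adverse events.
- **Type of estimate.** SAP Appendix A, on frequency tables: "Percentages should be calculated using this total as the denominator". The total is a count of patients; no person-time denominator appears anywhere.
- **Window.** SAP 4.4.4: an event on or after C1D1 and "up to the End-of-Treatment visit following discontinuation of the last study drug is considered treatment-emergent". Protocol 6.3 puts that visit 30 ± 7 days after the last dose of either drug, or before new antileukemic therapy if sooner. SAP 4.4.4 also excludes events after such therapy starts.
- **Tables.** SAP Section 10 lists 14.3.1.2 as "Treatment-Emergent Adverse Events by System Organ Class, Preferred Term (All Cycles), Safety Population: Phase 1b", and 14.3.1.3 to 14.3.1.9 carry the same All Cycles label. Table 14.3.1.1, "Overview of Treatment Emergent Adverse Events, Safety Population: Phase 1b", has no such label but no fixed window either.
- **Order of enrolment.** Protocol 4.1: the patients in a cohort, apart from those stopped by a DLT, "must complete the DLT assessment period before a decision to begin testing the next higher dose".
- **Termination.** SAP Section 7 records the sponsor's "decision to terminate the trial at completion of Phase 1b". Protocol 13.0 lists sponsor discontinuation of the trial as a reason to stop study treatment.
- **Related output.** SAP 6.4 summarises exposure (Table 14.1.4.1). SAP 6.6.2 summarises DLTs, which have a Cycle 1 window, but Section 10 lists no DLT table.

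**The concern.** The chance that a patient has at least one recorded event rises with the length of that patient's window. If two dose groups have different window lengths, their crude percentages differ even when the underlying hazard is the same. A true dose gradient can be flattened, exaggerated or reversed.

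There are two routes to unequal windows. First, cohorts open in ascending order, so a sponsor cutoff can fall earlier in treatment for patients enrolled later. Second, patients at one dose may stop sooner because of toxicity or progression, which needs no termination at all.

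Phase 2 was not enrolled, so these tables are the trial's only planned TEAE summaries by dose for the combination. The protocol's own background (2.2.1) relays a comparison in which severe and serious events were less frequent with gilteritinib "than in the chemotherapy groups when adjusted for therapy duration". It also quotes unadjusted percentages. The issue is therefore familiar in this setting, although that passage does not prescribe a method for this trial.

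**Working it through.** The documents give no adverse event rate, no exposure by cohort and no cutoff date. There is no plan figure to reproduce, and what follows is an illustration under stated assumptions.

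**Inputs**
- Median time on treatment 3.6 months, assumed exponential. This is the gilteritinib 120 mg figure in Protocol 2.5.1, used as a proxy. μ = ln 2 / 3.6 = 0.1925 per month.
- Tail after last dose f = 30 days = 30/30.4375 = 0.986 months, assuming no earlier new therapy.
- DLT period 28 days (Protocol Appendix 1). The minimum lag from Cohort 1 to Cohort 4 is 3 × 28 = 84 days (2.8 months), or 168 days if each cohort needs two successive groups of three.
- First-event hazard λ constant, set at 0.0989 per month so that incidence without a cutoff is 40%.

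**Formula.** With treatment cut at c months after enrolment and s = λ + μ:

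P(c) = 1 − e^(−λf) × [ (μ/s)(1 − e^(−sc)) + e^(−sc) ]

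With no cutoff, P = 1 − e^(−λf) × μ/s = 1 − 0.907 × 0.661 = 0.40.

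Worked case, c = 2: e^(−sc) = 0.558. The bracket is 0.661 × 0.442 + 0.558 = 0.850, and P = 1 − 0.907 × 0.850 = 0.229.

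**Same hazard, treatment cut at c.** The front-loaded column comes from simulation with cumulative hazard proportional to the square root of time, also set to 40% without a cutoff.

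| Cut (months) | Constant hazard | Front-loaded hazard |
|---|---|---|
| 0.92 (28 days) | 16.5% | 26.8% |
| 2 | 22.9% | 31.0% |
| 3.68 (112 days) | 29.5% | 34.8% |
| 6 | 34.7% | 37.4% |
| 12 | 39.1% | 39.5% |

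**Masking.** Doubling the hazard (λ = 0.1978) gives 59.4% without a cutoff but 40.3% if cut at 2 months, which is indistinguishable from the 40% group. A hazard ratio of 1.5 gives 51.2% without a cutoff and 40.5% if cut at 3.68 months.

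**No termination.** Halving median treatment time to 1.8 months (μ = 0.385) at the same λ gives 1 − 0.907 × 0.796 = 27.8% instead of 40%.

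**Backfill.** Take a lower-dose group with 6 early patients (no cutoff) and 14 backfill patients cut at 2 months like the higher-dose group: (6 × 40 + 14 × 22.9)/20 = 28.0%. The gap is 28.0 − 22.9 = 5.1 points, against 40 − 22.9 = 17.1 without backfill.

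**Common window.** Over the first 28 days, 1 − e^(−0.0989 × 0.92) = 8.7% in both groups, whatever the cutoff, for patients followed through Cycle 1.

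**Exposure-adjusted rate.** With constant hazard it equals 0.0989 per patient-month in both groups. With the front-loaded hazard it errs the other way: about 0.18 in a group cut at 28 days against 0.13 in one cut at 112 days, 39% higher at identical hazards.

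**The case against.** A reader might infer that the higher-dose cohorts did have shorter windows and so will look safer than they are. The documents do not show this. They give no cutoff date, no count of patients on treatment at termination and no exposure by cohort. SAP Section 7 calls the fourth cohort potential, so 90 mg may not have been enrolled. Backfill allows up to 20 patients at a cleared dose while a higher dose is under evaluation. Phase 1b may enrol up to 69 patients, while 3+3 over four doses needs at most 4 × 6 = 24 DLT-evaluable patients. Backfill could therefore be the majority, and lower-dose patients could be cut as early as higher-dose ones, or earlier. This stands, and it removes any claim about direction.

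A reader might also infer that the MTD/RP2D choice is distorted. It is not affected by this route: the Dose Escalation Committee decides after each cohort's DLT period (Protocol 4.1 and 17.1), whereas these tables belong to the final analysis at End of Study.

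The remaining points stand in part. The plan is descriptive, and with cohorts of 3 to 20 sampling error is large (exact 95% interval for 2/6: 4% to 78%; for 8/20: 19% to 64%). But sampling error does not excuse a systematic difference that can be avoided. Exposure will be summarised, which would reveal unequal treatment time but corrects no event percentage. The DLT summary has a fixed window but is narrow: it omits most lower-grade events, fatigue, and in general infection and febrile neutropenia.

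**Conclusion.** The point holds as a gap in the reporting plan. Crude TEAE percentages by dose rest on patient-specific windows, nothing in the plan makes those windows equal across dose groups, and no TEAE table uses a common one. The percentages may therefore not be comparable across doses.

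Neither the direction nor the size can be established from the documents. Under the assumptions above (3.6-month median as proxy, 40% event, 30-day tail, no backfill), the artefact is 17.1 points for a cut at 2 months, 5.3 at 6 months (40 − 34.7) and about 1 at 12 months. It is smaller if events are front-loaded (9.0, 2.6 and 0.5 points) or if backfill patients share the cutoff.

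What is at stake is the final presentation and interpretation of the primary safety endpoint by dose. A low-cost improvement is warranted; no conclusion that any dose was misjudged is.

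**What to change.** In SAP 6.6.1 and Section 10:

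1. Add Cycle 1 versions of Tables 14.3.1.2, 14.3.1.4 and 14.3.1.5 by dose group, with onset from C1D1 through the C2D1 pre-dose assessments. Base descriptive comparisons between doses on these.
2. Present exposure by dose group, including the number still on treatment at termination, alongside the All Cycles tables. Add a footnote that observation windows differ between patients and may differ between dose groups.
3. Optionally, add exposure-adjusted incidence rates as supplementary output only, with a note that they assume a roughly constant event rate.

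The cost is SAP wording and a few repeat table runs on data already collected, with no new patients, visits or procedures. Cycle 1 tables do not capture late-onset events, so the All Cycles tables should stay. The Cycle 1 window is also incomplete for patients who die or start new antileukemic therapy within it, so it removes most of the unequal-window problem rather than all of it.

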3. OBJECTIVES AND ENDPOINTS

Phase 1b: Dose Escalation

Objectives:	Endpoints:
Primary:	
To evaluate the safety of lanraplenib (LANRA) in combination with the FMS-like tyrosine kinase 3 (FLT3) inhibitor gilteritinib, in patients with relapsed/refractory (R/R) FLT3 -mutated AML.	Type, incidence, severity, causality, and outcome of adverse events (AEs), including serious and Grade ≥ 3 AEs; DLTs; MTD/RP2D of LANRA in combination with standard doses of gilteritinib.
Secondary:	

To characterize the pharmacokinetics (PK) of LANRA alone and in combination with gilteritinib.
 
To characterize the PK of gilteritinib when administered in combination with LANRA.
 
To evaluate preliminary antileukemic activity of the combination in patients with R/R FLT3-mutated AML.
	
Standard PK parameters including (but not limited to) maximal plasma concentration (C_{max}), time to maximal plasma concentration (T_{max}) and area under the plasma concentration x time curve from hour 0 to the last measurable time point (AUC_{0-last}).
 
Composite CR rate including CR and CRh as defined by ELN 2017 criteria (Döhner 2017).
 
Duration of response, defined as the time from first qualifying response (CR/CRh) until relapse or death from any cause, as assessed by study investigators.
 
Event free survival, defined at the time from treatment onset until treatment failure (i.e., failure to achieve CR/CRh), relapse from CR/CRh, or death from any cause.
 
Overall survival defined as the time from enrollment until death from any cause.

Exploratory:	

To assess the incidence of FLT3 measurable residual disease (MRD) negativity (if any) in bone marrow and peripheral blood among patients who achieve CR/CRh.
	
Assessment of MRD in bone marrow and peripheral blood beginning with the 1st bone marrow examination indicating CR/CRh using a molecular characterization platform (eg, reverse transcriptase polymerase chain reaction [RT-PCR]; next generation sequencing [NGS]).
 
Level of concordance for MRD in bone marrow aspirate and peripheral blood in patients with CR/CRh.

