4.4.4.2. Missing Data

Every effort will be made to obtain required data at each scheduled evaluation from all enrolled patients. See [Section 4.4.4.4](#) for details of imputing missing dates. AEs with missing causal relationship will be assessed as related to study treatment. AEs with missing severity will be included in the denominator for all grade events of the same preferred term (PT) but will not be included in the numerator for any severity when reporting the frequency of events by severity.

Unless otherwise specified, all other missing data will not be imputed.

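### The Phase 1b primary endpoint includes Grade ≥3 adverse events, but the SAP's only severity-restricted AE table stops at Grade 4, and no specified output counts patients with any Grade ≥3 TEAE

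*SAP*

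**What the plan says.** SAP section 3 gives the Phase 1b primary endpoint as "Type, incidence, severity, causality, and outcome of adverse events (AEs), including serious and Grade" 3 or above, together with DLTs and the MTD/RP2D. Protocol 3.1 has the same endpoint.

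For the analysis, SAP 6.6.1 lists "Separate summaries of Grade 3 and 4 treatment-emergent adverse events", and the table list in SAP section 10 carries this through as 14.3.1.4: "Grade 3 or 4 Treatment-Emergent Adverse Events by System Organ Class, Preferred Term and Greatest Severity". The other AE tables (all TEAEs, non-serious, serious, treatment-related, dose reduction, discontinuation, death) show no restriction or split by grade in their titles.

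Fatal events have a table of their own, 14.3.1.9: "Treatment Emergent Adverse Events Leading to Death by System Organ Class, Preferred Term (All Cycles), Safety Population: Phase 1b". There is also an overview, 14.3.1.1: "Overview of Treatment Emergent Adverse Events, Safety Population: Phase 1b". Its rows are not given.

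SAP 6.6.1 has two counting rules. For repeated events under one preferred term, "the event of greatest severity will be assigned to the preferred term for the appropriate summaries". A patient with several terms in one system organ class "will be counted once at the system organ class level"; nothing is said there about which grade that patient carries.

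**The concern.** Grade 5 is on the SAP's own severity scale (SAP 6.6), and Protocol 16.7.2 has a fatal event recorded as that event at Grade 5. Grade ≥3 and Grade 3 or 4 are therefore different sets, and the difference is the most severe events. A term that worsens from Grade 4 to fatal takes Grade 5 under the worst-grade rule and leaves the one table that reports by severity.

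At stake is a clear figure for a named part of the primary endpoint. A reader of the Phase 1b report who takes the Grade 3/4 patient count as the Grade ≥3 count has a lower bound. Dose cohorts are small, so one patient can move a percentage visibly.

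**Working it through.** The plan gives no figure to reproduce. The check compares the endpoint with the planned outputs and then works through the counting.

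**Step 1. Endpoint against outputs.**
- Endpoint (SAP 3, Protocol 3.1): Grades 3, 4 and 5.
- Severity-restricted AE summary (SAP 6.6.1, Table 14.3.1.4): Grades 3 and 4.
- Grade 5: reached through the death table, 14.3.1.9, which is defined by outcome.
- SAP 4.4.4.2: an AE with missing severity "will not be included in the numerator for any severity when reporting the frequency of events by severity". Reporting by severity is thus expected and not confined to Grades 3 and 4, but no table is named.
- A specified count of patients with any Grade ≥3 TEAE: none found in the text or the table titles.

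**Step 2. Preferred-term level.** If the worst grade is taken first and the Grade 3/4 filter applied second, a patient is in 14.3.1.4 or in 14.3.1.9 for a given term, not both. Provided every fatal TEAE is graded 5, the two counts add to the Grade ≥3 count for that term.

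**Step 3. SOC and overall level.** Consider a patient with a Grade 3 or 4 event under one term and a fatal event under another term in the same SOC.
- If worst grade is applied per patient within the SOC, the patient is Grade 5 there, appears only in 14.3.1.9, and the tables add exactly.
- If worst grade is applied per term only, the patient is counted once in each table, and the sum counts that patient twice.

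The title of 14.3.1.4 is compatible with the first reading. The text of 6.6.1 states the rule only for terms. The same holds for an overall patient row.

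**Step 4. Bound on the second reading.** Let A be the patients with a Grade 3/4 TEAE and D the patients with a fatal TEAE. The number with any Grade ≥3 TEAE is A + D minus the overlap, and the overlap lies between 0 and min(A, D). Hence

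max(A, D) ≤ patients with any Grade ≥3 TEAE ≤ A + D.

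Illustration with assumed counts, in a dose cohort at the cap of 20 patients (SAP 2.1): A = 12 and D = 3 give between 12/20 = 60% and 15/20 = 75%. The two tables alone do not say where in that range the answer lies; Listings 16.2.7.1 to 16.2.7.3 do.

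**Step 5. Table 14.3.1.4 used alone.** Let f be the patients whose only Grade ≥3 event is Grade 5. On the per-term reading the Grade 3/4 patient rate falls short of the Grade ≥3 rate by f/N. The values of f are assumed; N = 6 is a full 3+3 cohort, N = 20 the cohort cap (both SAP 2.1), and N = 69 the Phase 1b maximum (SAP 4.2).

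| N | f = 0 | f = 1 | f = 2 |
|---|---|---|---|
| 6 | 0 | 1/6 = 16.7 points | 2/6 = 33.3 points |
| 20 | 0 | 1/20 = 5.0 points | 2/20 = 10.0 points |
| 69 | 0 | 1/69 = 1.4 points | 2/69 = 2.9 points |

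If worst grade is applied per patient overall, every patient with a Grade 5 event leaves the Grade 3/4 count, and the shortfall is D/N instead.

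**The case against.** The strongest reply is that every Grade ≥3 event is already tabulated. Grades 3 and 4 are in 14.3.1.4, and deaths are in 14.3.1.9, which is in substance the Grade 5 table. Fatal TEAEs also enter the all-TEAE and serious-TEAE tables and the listings. This stands. A reader might infer that deaths drop out of the safety report; the documents do not support that.

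Second, the title of 14.3.1.4 can be read as applying greatest severity at SOC level. This also stands. A reader might infer that the two tables can never be added above term level, but that follows only from the per-term reading. What remains is that 6.6.1 does not settle which reading applies.

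Third, the endpoint defines no proportion, and SAP 4.1 makes all testing descriptive. That limits the weight of the point, but incidence and Grade ≥3 AEs are both named in the endpoint, and a patient count is the ordinary way to report them.

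Fourth, section 10 lists proposed titles, and overview Table 14.3.1.1 could carry the row. So the count can be called unspecified; it cannot be said that it will be absent from the report.

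Finally, Protocol 2.2.1 reports Grade ≥3 febrile neutropenia in 45.9% and anemia in 40.7% of gilteritinib patients in the Phase 3 trial. Many patients with a fatal event may therefore also have a Grade 3/4 event, which would make f small. This is reasonable, although it does not give f and does not reduce D.

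**Conclusion.** The point holds as a minor reporting error. The filter in SAP 6.6.1 and Table 14.3.1.4 does not match the primary endpoint, and no specified output gives the number of patients with any Grade ≥3 TEAE by dose level.

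The size is unknown, because the documents give no Grade 5 rate. The percentages above rest on assumed counts and show only how much one or two patients weigh at each N. A reader might take the 33.3 points at N = 6 as a likely error; nothing in the documents supports that.

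The bound assumes that fatal TEAEs are graded 5, as Protocol 16.7.2 indicates. The data are collected and listed, and the count can be derived from the listings. No dose decision depends on it. SAP section 7 restricts all analyses to Phase 1b because Phase 2 was not enrolled, so the effect is confined to that report.

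**What to change.** - In SAP 6.6.1 and the title of Table 14.3.1.4, replace the Grade 3 and 4 / Grade 3 or 4 limit with *Grade ≥3 (3, 4 or 5)*.
- State that worst grade is applied per patient at term, SOC and overall level.
- Include a row for patients with *any Grade ≥3 TEAE*, by dose level and overall.
- Keep Table 14.3.1.9 as the separate account of deaths.
- Leave SAP 6.6.3 and Table 14.3.2 unchanged: the laboratory grading in Appendix B has no Grade 5.

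The cost is one wording edit with a sentence on the counting rule, one table title with its filter, and one added row. No new data are needed.
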